### **12) Stopping rules.**

The following events will require the study to pause and be evaluated prior to resuming the study. These events will be reported to the FDA in a timely manner as required per 21 CFR 312.64(b)

- a. Any major bleeding event
- b. Any anaphylaxis event
- c. 2 infusion reactions

**13) Risks to Subjects\***

Hypersensitivity reactions, including anaphylaxis, are possible. Should symptoms occur, THROMBATE III infusion will be discontinued and appropriate treatment begun as per clinical judgement.

- Because THROMBATE III is made from human blood, it may carry a risk of transmitting infectious agents, e.g., viruses, the variant Creutzfeldt-Jakob disease (vCJD) agent and, theoretically, the Creutzfeldt-Jakob disease (CJD) agent.
- We will perform coagulation tests to avoid excessive or insufficient anticoagulation and monitor for bleeding or thrombosis. Assessment will be based on clinical findings at the discretion of the treating physician along with laboratory values of PT, PTT, Hemoglobin and Hematocrit analysis. Treatment may include heparin for excessive coagulation or blood transfusion for insufficient coagulation ultimately left to the discretion of the treating physician.

Two clinical trials were conducted in 33 subjects with congenital AT deficiency. Nine subjects (27%) experienced 29 adverse reactions which occurred during 17 of 389 infusions. There were no serious adverse reactions reported. The severity of adverse reactions was reported as mild or moderate, except for wound secretion and hematoma, which was severe.

Dizziness (12%), Chest discomfort (9%), Nausea (9%), Dysgeusia (6%), Pain (cramps) (6%), and each of the following were reported in 3% of the subjects: Chills, Wound secretion and hematoma, Vision blurred, Chest pain, Dyspnea, Intestinal dilatation, Pyrexia and Urticaria,

**DRUG INTERACTIONS**

The anticoagulant effect of heparin is enhanced by concurrent treatment with THROMBATE III in patients with hereditary AT deficiency. Thus, in order to avoid bleeding, the dosage of heparin (or low molecular weight heparin) may need to be reduced during treatment with THROMBATE III.

The effect of drugs that use antithrombin to exert their anticoagulation may be altered when THROMBATE III is added or withdrawn. We will regularly perform coagulation tests suitable for the anticoagulant used (e.g., aPTT and anti-Factor Xa activity) and at close intervals to avoid excessive or insufficient anticoagulation. Adjust dosage of anticoagulant as necessary. Additionally, we will monitor the patients for the occurrence of bleeding or thrombosis.

**14) Potential Benefits to Subjects\***

We expect subjects with deficient endogenous AT3 can lessen the risk associated with a prothrombotic hyperinflammatory state with infusion of AT3.

**15) Setting:** Jackson South Medical Center , Jackson Memorial Hospital

**16) Resources Available**

The PI has experience conducting and being trained for clinical research. All study personnel will be trained on the protocol by the investigator or designee and complete CITI training. Those obtaining consent will also have prior experience communicating with patients.

**17) Prior Approvals:** We have preliminary approval of funding from Grifols.

**18) Confidentiality**

The protected health information collected for the purpose of this research study will be assigned a research code number and any obvious patient identifiers (name, social security number, hospital record number) will be removed from this information. Both the confidential health information and the information linking the research code numbers to the patients' identities will be stored in a secure manner (e.g., locked file cabinet, password protected database) accessible only to the study team. The information linking the research code numbers to the patients' identities will be stored separate from the confidential health information.

Data will be de-identified and stored on a password-protected network accessible only to research staff. Data will be retained for at least six years following conclusion of the study on this network.

*Please note: Any data, including Personally Identifiable Information (PII) and/or Protected Health Information (PHI), acquired from JHS with a waiver of HIPAA Authorization (without a signed HIPAA authorization) may only be stored in the secure JHS SharePoint environment provided by JHS. The Study Team is not permitted to copy or store JHS data in any other system. We will contact the JHS Office of Research for additional information or clarification.*

*Protected Health Information (PHI) is defined under HIPAA in 45 CFR § 160.103. The following list of identifiers of an individual, or of relatives, employers, or household members of the individual, are defined under HIPAA in 45 CFR § 164.541:*

*(A) Names;*

*(B) All geographic subdivisions smaller than a State, including street address, city, county, precinct, zip code, and their equivalent geocodes, except for the initial three digits of a zip code if, according to the current publicly available data from the Bureau of the Census:*

*(1) The geographic unit formed by combining all zip codes with the same three initial digits contains more than 20,000 people; and*

*(2) The initial three digits of a zip code for all such geographic units containing 20,000 or fewer people is changed to 000.*

*(C) All elements of dates (except year) for dates directly related to an individual, including birth date, admission date, discharge date, date of death; and all ages over 89 and all elements of dates (including year) indicative of such age, except that such ages and elements may be aggregated into a single category of age 90 or older;*

*(D) Telephone numbers;*

- (E) Fax numbers;
- (F) Electronic mail addresses;
- (G) Social security numbers;
- (H) Medical record numbers;
- (I) Health plan beneficiary numbers;
- (J) Account numbers;
- (K) Certificate/license numbers;
- (L) Vehicle identifiers and serial numbers, including license plate numbers;
- (M) Device identifiers and serial numbers;
- (N) Web Universal Resource Locators (URLs);
- (O) Internet Protocol (IP) address numbers;
- (P) Biometric identifiers, including finger and voice prints;
- (Q) Full face photographic images and any comparable images; and
- (R) Any other unique identifying number, characteristic, or code

The name, date of birth and mrn are required to conduct this study.

**19) Choose the statements below that are applicable to this research:**

20(a). Will the research collect protected health information or personally identifiable information from the EMR or from subjects at UHealth and/or JHS?

- Yes (If checked go to 21(b))
- No (If checked, go to Section 22)

20(b). Check the box next to the correct statement below

- Research Subjects will sign a HIPAA Authorization before the research will collect this data.
- Research Subjects will not sign a HIPAA Authorization for this data collection and the
- Research is requesting a waiver of HIPAA authorization from the IRB. (If checked, complete Section 17 below)

20(c). How will the research store the data? (See Section 21(e) below)

- On a University of Miami electronic device (e.g. encrypted, password-protected computer)
- On a cloud-based storage system that is approved by the University of Miami
- On a secured JHS SharePoint environment (required for protected health information or identifiable information collected from JHS records without a waiver of authorization from IRB.)
- Other, specify: Click here to enter text.

20(d) Select one of the following:

- The Principal Investigator (and/or Study Team members) will record (e.g. write down, abstract) data acquired in a manner that does not include any indirect or direct identifiers (listed in the instructions for Section 19 of this protocol), and the recorded data will not be linked to the individual's' identity.

OR

- The Principal investigator (and/or Study Team members) will record (e.g. write down, abstract) the data collected in a manner that does not include any direct identifiers (see list in the instructions for

Section 19 (Confidentiality) of this protocol) of any subject. Instead, the Principal Investigator and/or Study Team members shall will assign a code (that is not derived in whole or in part from any direct or indirect identifiers of the individual) to each study subject and link the code to the study subject's identity. The link to each subject's identity and/ or other identifiable information will be maintained on a document separate from the research data.

**20(e) Additional requirement for Jackson Health System Data:**

This section applies to data that will be collected from JHS under a waiver of HIPAA authorization (without a signed HIPAA Authorization from the participant).

Not-applicable, no data will be acquired from JHS under a waiver of authorization.

JHS data, including Protected Health Information (PHI) and/or Personally Identifiable Information (PII), acquired from JHS for this research under a waiver of authorization shall only be stored on the secured JHS SharePoint environment made available by JHS. I and the Study Team members shall not copy or store the JHS sourced personally identifiable information (PII), including protected health information (PHI) data to any other system, including any systems maintained or provided by the University of Miami. I and the Study Team shall only copy or transfer JHS-sourced data that has been properly de-identified in accordance with all requirements contained in the HIPAA Rules by removing all of the identifiers listed in the instructions for Section 19 of this protocol.

**20) Provisions to Protect the Privacy Interests of Subjects**

Access to patients and their protected health information along with the collection and analysis is necessary in order to conduct this research study. Consistent with the "minimum necessary standard" of the HIPAA privacy rule, we will only access and collect the specific health information necessary to complete this research study.

Some of the research investigators who will access and use the protected health information may also be involved directly in the care of the respective patients, thus obviating the privacy and confidentiality concerns.

Authorization to obtain protected health information will be obtained from the patient as soon as possible.

The protected health information collected for the purpose of this research study will be assigned a research code number and any obvious patient identifiers (name, social security number, etc) will be removed from this information. Both the confidential health information and the information linking the research code numbers to the patients' identities will be stored in a secure manner (e.g., locked file cabinet, password protected database) accessible only to the study team.

**21) Consent Process**

**22a. Remote Consenting for subject proxies unavailable for inperson consenting will includethe following:**

- Send a copy of the consent document via secure email or U.S. Mail.
- Arrange for an impartial witness not part of the study team to attend and witness the consent discussion.

- Let the participant know that a witness will join the consent meeting.
- Set up a video meeting or 3-way call and send an invitation to the attendees.

We will ask the participant to scan or take a picture of each page of the documents and email the signed/dated documents to the study team. As an alternative, we may establish a secure network location for uploading the consent document.

During meeting:

- Identify everyone on the call.
- Review the informed consent with the participant, answer the participant's questions and ask questions of the participant to confirm comprehension.
- Ask the participant if s/he consents to participate/continue participation.
- If the participant agrees, ask him/her to sign and date the consent document.
- If using 3-way call, ask the participant to confirm s/he signed & dated the document.

We will ask the participant to scan or take a picture of each page of the documents and email the signed/dated documents to the study team. As an alternative, the research could establish a "UM Box" location for uploading the consent document.

If the person is unable to take a picture, we will document the circumstances.

The person conducting the consent process will sign and date a copy of the consent document.

The impartial witness will sign & date on the witness line of a copy of the consent document.

The person conducting the consent process will document the purpose for the remote consent (COVID-19), and each step of the process. The note will explain why the research team doesn't have the signed and dated document.

#### Documenting the Remote Consent process

The originals of the informed consent document signed by the investigator (and possibly the witness) will be placed in the participant's research record.

The person obtaining consent will document how s/he confirmed that the patient consented and signed the consent form. The participant may retain the signed original due to contamination. The note will include a statement indicating why the informed consent document signed by the participant was not retained, (e.g., due to contamination of the document by infectious material.)

If the participant cannot send a picture of the signed document, the person obtaining consent will document why a copy of the signed document is not available. See example below.

Example:

Informed consent was obtained on Date at Time. The participant could not come to the site for the consent process due to COVID-19 social distancing requirements. A copy of the consent document was emailed to the prospective participant before the consent discussion

The consent process was performed by phone/ZOOM. The individuals attending the discussion were: (list the names of the individuals). The person obtaining consent explained the research to the participant and answered the participant's questions. The person obtaining consent asked the participant questions to ascertain whether the s/he understood the study, and the participant was able to answer the questions. The participant voluntarily agreed to participate. The subject/LAR signed and dated the consent document. The research was not able to obtain a copy of the signed original consent document because consent was obtained remotely, and the document may transmit the COVID-19 infection.

After signing the consent document, the participant took a picture and sent it to the research team/ OR The participant was unable to send a picture of the document. An impartial witness observed the entire process.

The consenter will then add similar documentation about the HIPAA authorization.

**22b. In person consenting:**

The subject will be approached in the clinic area by a member of the research staff. Any of the staff members listed on the protocol will discuss the risks and benefits of participation. If the staff member is not fluent in the patient's preferred language, they will use a translator to obtain informed consent in a document written in the patient's preferred language. Initiating this process may also occur over the phone and during scheduling and may include mailing of the consent form to allow for more time to read and understand prior to coming into clinic.

Subject will be given an ICF in their preferred language (English/Spanish only). They will be given ample time to review the ICF with family, clergy, friends or primary physicians. Once they have agreed they will be required to sign ICF before any study procedures can be done on the subject. A copy of the ICF will be given to the subject and one will be placed in the medical records. The original will stay in the subject's source documentation folder located in the Trauma Research Office.

**22) Process to Document Consent in Writing**

We will document consent with a translated written informed consent document in a language understandable to the participant. If subjects who do not speak English are eligible, we ensure that the oral and written information provided to those subjects will be in that language either by research personnel fluent in that language or by an institutional translator. We will pursue approval of the consent documents in Spanish as a significant portion of the subject population may speak Spanish. We also request permission to utilize the short forms for documentation of consent and translation into other than the English or Spanish for the rare circumstance that the subject cannot communicate in either of those languages.

**23) Authorization for Use and Disclosure of Protected Health Information (HIPAA)**

Type of Request:

- Waiver of Authorization for access to medical record for subject identification/recruitment.
- Waiver of Authorization for access to medical record to obtain data for the research.

UM IRB# 20201048

AT3 in COVID-19  
January 24, 2022, Version 6.2

Confirm that you will destroy the Protected Health Information (PHI) you and/or your Study Team acquire receive from JHS and/or UHealth at the earliest opportunity.

**I confirm**

Confirm that the Protected Health Inform (PHI) you acquire from JHS and/or UHealth will not be re-used or disclosed to any other person or entity, except as required by law or for authorized oversight of the research study or for other research for which the use or disclosure of PHI is permissible.

## **24) Drugs or Devices**

### **Drug Administration, Dispensation and Disposition**

Once consent is obtained and necessary baseline data collected, and if the subject is enrolled and falls into the Thrombate III infusion arm, they will begin receiving THROMBATE III (Antithrombin III [Human]) at 120% target dose every other day for 9 days.

Study drug will be packaged, labeled, and delivered to the clinical center by the drug manufacturer. All medication supplied to be used in this study will be manufactured, tested, labeled, and released according to current legal requirements and Good Manufacturing Practice (GMP).

The pharmacy will conduct an inventory upon receipt of the clinical supplies and will acknowledge receipt of the supplies to the sponsor. A copy of the shipping documents will be maintained for records. Study drug will be stored in accordance with the package insert in a secure location until dispensed to the subject.

Study drug kits will be dispensed according to the dosing schedule. The pharmacy will keep a current record of the inventory and dispensing of all clinical supplies. This record will be made available to the sponsor's monitor for the purpose of accounting for all clinical supplies. Any discrepancy or deficiency will be recorded, with an explanation. All supplies sent to the investigator will be accounted for and in no case will clinical supplies be used in an unauthorized situation.

**Appendix A**

**ISTH DIC**, the score is increased by 2 points for abnormal baseline D-dimers (fibrin-related marker) and/or abnormal fibrinogen <1.0 gram/L level (1 point). This scoring algorithm was developed by the ISTH Scientific and Standardization Committee (SSC) committee on DIC and published in 2001. The ISTH DIC is a set of objective criteria for the diagnosis and severity of DIC with a score of  $\geq 5$  correlating with overt DIC, whereas < 5 does not rule out DIC but may indicate DIC that is not overt. The score is only appropriate for use in patients with an underlying disorder that is known to be associated with DIC; e.g., sepsis, severe immunological reactions, etc.

The ISTH DIC score is calculated using

- platelet count ( $\geq 100,000 = 0$ ;  $50,000-99,999 = 1$ ;  $< 50,000 = 2$ ),
- fibrinogen level ( $\geq 100 \text{ mg/dL} = 0$ ;  $< 100 \text{ mg/dL} = 1$ ),
- prothrombin time prolongation above upper limit of normal (ULN)
  - ( $< 3 \text{ seconds} = 0$ ,  $3-6 \text{ seconds} = 1$ ,  $> 6 \text{ seconds} = 2$ ),
- and D-dimer ( $< 2 \text{ times ULN} = 0$ ,  $2-4 \text{ times ULN} = 2$ ,  $> 4 \text{ times ULN} = 3$ ).

**SOFA SCORE**

SOFA SCORE (Sequential Organ Failure Assessment)					
ORGAN SYSTEM	0	1	2	3	4
Respiratory* PaO 2 / FIO 2 Ratio	> 400	$\leq 400$	$\leq 300$	$\leq 200 \text{ w/support}$	$\leq 100 \text{ w/support}$
Hematologic Platelets	> 150	$\leq 150$	$\leq 100$	$\leq 50$	$\leq 20$
Hepatic Serum Bilirubin	< 1.2	1.2 – 1.9	2.0 – 5.9	6.0 – 11.9	> 12.0
CV MAP	No hypotension	< 70	Dopamine $\geq 5$ or Any dobutamine	Dobutamine > 5 or Epi $\leq 0.1$ or Norepi $\leq 0.1$	Dopamine > 15 or Epi > 0.1 or Norepi > 0.1
Neurologic* Glasgow Coma Score	15	13-14	10-12	6-9	< 6
Renal Serum Creatinine	< 1.2	1.2 – 1.9	2.0 – 3.4	3.5 – 4.9 or $< 500 \text{ u/o}$	> 5 or $< 200 \text{ u/o}$

\*See Appendix D. A Modified GCS is provided for intubated patients. Also provided for cases when it is not possible to obtain arterial blood gases to determine the SOFA respiratory parameter, SpO2/FiO2 ratio can be imputed for PaO2/FiO2 ratio. For patients on supplemental oxygen via nasal cannula, nasopharyngeal catheter or mask and for converting SpO2 values to PaO2 see Appendix D for oxygen conversion tables.

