**8) Procedures Involved\***

Any member of the study team will discuss potential subjects with the clinical team for appropriate pursuit of informed consent and screening for eligibility.

75 eligible subjects, after consent, will have laboratory blood tests for further screening.

25 of those subjects with endogenous **AT3  $\geq$  100%** will continue with SOC.

50 of those subjects with endogenous **AT3 < 100%** will be will be randomly assigned to begin **SOC plus treatment with exogenous AT3 supplementation or only SOC** treatment. The randomization schedule will be established by a member of the study team that is not involved in the informed consent process.

They will all be followed up for laboratory blood tests, study endpoints and adverse events. If they do not meet entry criteria they will be excluded from the study.

[figure not shown]
Consented subjects will be scored according to The International Society of Thrombosis and Haemostasis Disseminated Intravascular Coagulation scale (ISTH DIC) on study visit days 1, 3, 5, 7, 9 and 11.

The SOFA score will be performed only when the parameter is obtained clinically and monitored for changes in patient status on study visit days 1, 3, 5, 7, 9 and 11. Each organ system is assigned a point value from 0 (normal) to 4 (high degree of dysfunction/failure). It will be calculated on admission and Day 11 using the worst parameters measured during the study visit day. If a parameter is not obtained clinically it will be voided for research purposes.

UM IRB# 20201048

AT3 in COVID-19  
January 24, 2022, Version 6.2

After enrollment and each 48h period (+/- 12 hours) thereafter, blood samples are collected and assayed for routine clinical coagulation and inflammation markers, including AT3 activity, D-Dimer, anti-Xa, fibrinogen, and prothrombin time until Day 11.

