## **9) Statistics\***

Statistical analyses will be performed using SPSS version 21 (IBM Corporation, Armonk, NY). Parametric data are reported as  $M \pm SD$  and nonparametric data are reported as median (interquartile range). Missing values for continuous variables are handled by applying imputation methods before calculating their statistics. The study population will be stratified into two halves based on the primary outcome of change from baseline SOFA and/or ICH DC. Those with the fastest rate of recovery are compared to those with the slowest rate of recovery. We expect that AT3 will correlate with rate of recovery and/or with one or more of the secondary outcomes. The demographics and physiologic variables in the fastest and slowest groups are compared using a t test or Mann-Whitney U-test, as appropriate. Categorical variables are compared using a  $\chi^2$  or Fisher's exact test, as appropriate. Statistical significance is determined at  $p < 0.05$ . Then multivariate models will be evaluated for predicting the primary or secondary outcomes, using various performance metrics, such as area under the receiver operating characteristic curve, sensitivity and specificity, positive predictive value, and negative predictive value, as we have described in multiple previous studies. In addition, propensity scores will be assigned for each patient based on a 1:1 fixed ratio nearest neighbor matching was performed to compare those with fastest or slowest recovery. A 1:1 fixed ratio nearest neighbor matching is performed to minimize bias without sacrificing power, as we have described in multiple previous studies.

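### The SOFA cardiovascular row lists dobutamine under two scores and leaves one dopamine range with no drug column; two laboratory boundaries are also open

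*Combined protocol and SAP*

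**What the plan says.** The cardiovascular row of the SOFA table in Appendix A reads as follows.

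- Score 0: "No hypotension". Score 1: MAP below 70.
- Score 2: "Dopamine $\geq 5$ or Any dobutamine". The second condition, "Any dobutamine", carries no dose limit.
- Score 3: "Dobutamine > 5 or Epi" or norepinephrine, each of the last two up to 0.1. There is no dopamine entry.
- Score 4: "Dopamine > 15 or Epi > 0.1 or Norepi > 0.1".

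No dose units are printed. The table's footnote helps with the respiratory and neurologic rows only.

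On how to score, Section 8 says: "It will be calculated on admission and Day 11 using the worst parameters measured during the study visit day". On missing items it says: "If a parameter is not obtained clinically it will be voided for research purposes".

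Section 7 and Appendix C list SOFA change from baseline as a secondary endpoint, and Section 7 makes the ISTH DIC score primary. Section 9 instead speaks of the "primary outcome of change from baseline SOFA and/or ICH DC".

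**The concern.** A scoring table should send each agent and dose to one score. Here dobutamine above 5 satisfies two cells, dopamine above 15 satisfies two cells, and one range of dopamine doses satisfies no drug cell. A patient on dopamine in the uncovered range with adequate MAP scores the same as an untreated patient, while any dobutamine dose scores at least 2.

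What is at stake is accuracy in a named secondary endpoint. Two assessors who read the row differently at two visits could record a change in SOFA when neither the drug nor the dose had changed.

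**Working it through.** The plan gives no power, effect size or standard deviation for SOFA, so there is no figure of its own to reproduce. The check is to treat each printed cell as a condition and list which cells each case meets. Doses are on the table's own unprinted unit scale.

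**Step 1. The row as printed (dopamine at or above 5 under score 2).**

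| Case | Drug columns met | Highest column met |
|---|---|---|
| Dopamine 3 | none | 0 or 1, by MAP |
| Dopamine 5 or 10 | 2 | 2 |
| Dopamine 20 | 2 and 4 | 4 |
| Dobutamine 3 | 2 | 2 |
| Dobutamine 8 | 2 and 3 | 3 |
| Epinephrine or norepinephrine 0.05 | 3 | 3 |
| Epinephrine or norepinephrine 0.2 | 4 | 4 |
| No drug | none | 0 or 1, by MAP |

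Overlaps: dobutamine above 5, 3 − 2 = 1 point; dopamine above 15, 4 − 2 = 2 points. Gap: dopamine above 0 and below 5.

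**Step 2. The same row with the score 2 dopamine sign reversed,** in case the PDF reading changed it. Dopamine 3 and 5 now score 2, dopamine 20 meets only column 4, and dopamine 10 meets no drug column. The gap moves to doses above 5 up to 15 and the dopamine overlap disappears. Dobutamine 8 still meets columns 2 and 3. So a dobutamine overlap and a dopamine gap exist under either sign.

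**Step 3. Does the rest of the table supply a rule?** Platelet cut-offs are nested (at or below 150, 100, 50, 20). A count of 15 meets columns 1, 2, 3 and 4, so the row works only if the highest column is taken. The PaO2/FiO2 row is built the same way. Applied to the cardiovascular row, that rule gives the last column of the Step 1 table: one score per case, but with dopamine 3 still scored on MAP alone.

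**Step 4. Laboratory boundaries.** Bilirubin cells run 6.0 to 11.9 (score 3), then above 12.0 (score 4); 12.0 is in neither. Creatinine cells run 3.5 to 4.9 (score 3), then above 5 (score 4); 5.0 is in neither, although urine output may still place the patient. Each is a 1-point question (4 − 3). The voiding rule does not help, because these values were obtained.

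**Step 5. Size per patient.** The overlaps are worth 1 or 2 points. For the gap, if the intended score is the lowest drug column (an assumption), the shortfall is 2 − 1 = 1 or 2 − 0 = 2 points. With the sign reversed, the uncovered doses lie between a score 2 range and a score 4 range, so the shortfall could be larger if a score above 2 is intended. The documents do not settle this.

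**Step 6. Size per group.** Section 4 gives 25 patients per group. If n patients are mis-scored by d points in the same direction at one visit, the group mean at that visit moves by n × d / 25. The number affected is not in the documents; assume 1 to 5.

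- Low end: 1 × 1 / 25 = 0.04.
- High end: 5 × 2 / 25 = 0.40.

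This carries into the change score only if the mis-scoring differs between baseline and follow-up. The same error at both visits cancels.

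**The case against.** The strongest reply is that the overlaps are ordinary. The table plainly works by taking the highest column met, and Section 8 tells assessors to use the worst parameters of the day. This largely stands for the overlaps. No sentence states it, however: the Section 8 wording selects which measurement to use, not which of two matching cells. The table also mixes nested rows (respiratory, platelets) with exclusive bands (hepatic, neurologic, renal). And the rule leaves the dopamine gap and the two boundaries open.

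A second reply is that the dopamine argument rests on one sign that PDF extraction may have changed. That is a fair caution about which range is uncovered, but Step 2 shows that one range is uncovered either way.

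Several stronger readings are tempting and are not supported:

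- A reader might infer that some patients cannot be scored on this row. MAP still gives patients in the gap 0 or 1; their drug support is simply not counted.
- A reader might infer that SOFA change cannot be computed consistently at all. Epinephrine, norepinephrine and no-drug cases are unaffected, and the other organ rows are untouched apart from the two boundary values. Multi-organ failure is an exclusion in Section 3, so few patients are likely to be involved.
- A reader might infer scoring that differs by arm because the trial is open label. Nothing in the documents indicates that vasoactive use or its scoring would differ by arm.
- A reader might treat this as a flaw in the primary endpoint because of Section 9. Section 7 names the ISTH DIC score; the Section 9 wording is a separate inconsistency.

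A larger obstacle to a Day 9 SOFA change is that the Appendix B flowsheet schedules SOFA only on Days 1 and 11. That is also a separate point.

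**Conclusion.** The cardiovascular row is internally inconsistent as written. Dobutamine falls under two scores, dopamine has no score 3 entry, and one dopamine range has no drug column whichever way the score 2 sign is read. Bilirubin 12.0 and creatinine 5.0 fall between cells.

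The effect is an error of 1 to 2 points per affected patient as the row is printed, in a secondary endpoint, for a number of patients that the documents do not give and that is probably small. The 0.04 to 0.40 shift in a group mean rests on the assumed 1 to 5 affected patients of 25, all mis-scored in one direction. The point deserves correction because the rule is wrong on its face and cheap to mend, not because it threatens the trial's main result. Which cell holds the error cannot be settled from the documents.

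**What to change.** - Reconcile the cardiovascular row with the SOFA version the trial intends to use, and name that version, so that each agent and dose range maps to one score.
- Print the dose units.
- State that the highest column met is the one scored.
- Close the bilirubin 12.0 and creatinine 5.0 boundaries.
- Re-score enrolled patients from existing records where infusion rates are available. Appendix B has concomitant medications recorded at every visit, but does not say whether rates are captured.

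The cost is one corrected table row, two boundary edits, one added sentence and some re-scoring. No new data collection is needed.
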